5.8 Intra-oral Appliance

The *in situ* model involves the placement of gauze-covered enamel specimens in the subject's mandibular partial denture (see Figure 1). The subject's denture will be prepared for the study by creating a hollow in the buccal flange area on one side of the partial denture and in the teeth of the same side large enough to accommodate the enamel specimens. Four gauze-covered enamel specimens (two 4 × 4 mm square and two 4 mm round) will be mounted on the partial denture as described previously. The enamel specimens will be mounted in such a manner that the gauze-covered enamel surface of the specimen is flush with the surface of the buccal flange/teeth of the subject's partial denture. The two square enamel specimens will be luted in place in the buccal flange area of the partial denture using a light-cured dental composite (Triad VLC material, Dentsply Int., York, PA). Great care will be taken to avoid contaminating the enamel surface of the specimens with the luting material. The round specimens placed in the buccal surface of the denture teeth will be mounted in place with DentuSil™ - Silicone Soft Reline Material (The Harry J. Bosworth® Company, Skokie, IL) or an equivalent material. The DentuSil™ material will be placed in the drilled sites and the enamel specimens carefully inserted so that they be mounted flush with the buccal surface of the denture teeth when fully seated. Again great care will be taken to avoid contaminating the enamel surface of the specimens with the luting material. Upon completion of the study the subject's partial denture will be repaired. The location where the enamel specimens will be placed on the subject's partial denture are not functional parts of the denture, and the experimental procedures will not cause any permanent damage to the denture.

Prior to placement in the subjects' partial dentures, all enamel specimens will be sterilized by exposure to ethylene oxide.

FIGURE 1

Lower Partial Denture Appliance with specimens placed in the buccal flange and buccal surface of posterior denture teeth

5.9 Adverse Events Assessment

Subjects will be questioned at each visit regarding any general health or oral complaints and symptoms they have experienced since baseline. Any findings will be documented on the AE CRF. In the event of subjects reporting AEs outside the scheduled clinical visit, they are assessed at the earliest opportunity by the Investigator.

All AEs, regardless of severity or relationship to the test product, will be recorded. Serious AEs include any events resulting in death, decreased life expectancy, life-threatening situations, persistent or permanent disability/incapacity, hospitalization, or congenital anomaly/birth defect. Within 24 hours, the Investigator will submit a written report documenting the circumstances of the serious AE.

6.0 LABORATORY METHODS

6.1 Specimen Preparation

Extracted human teeth will be used as the hard tissue test substrate for the preparation of the 4 x 4 mm specimens in the existing situ caries model. The teeth will be collected and transported to OHRI in a saturated thymol solution. Upon receipt, the teeth will be sorted and cleaned. The teeth will then be stored in saturated thymol solution during sample preparation procedures.

Teeth will be selected based on the following criteria:

- Free of caries and major restorations;
- No discoloration and no markings, such as cracks, when viewed under a microscope at 20× magnification;
- Sufficient tooth surface to provide a large size specimen to meet study requirements.

Bovine teeth will be used as the hard tissue test substrate for the preparation of the 4 mm round specimens in the modified in situ caries model. Upon receipt at OHRI, the teeth will be sorted, cleaned and stored in 0.1% thymol solution during sample preparation procedures.

Teeth will be selected based on the following criteria:

- Have no discoloration and no markings, such as cracks, when viewed under a microscope at 20× magnification.
- Sufficient tooth surface to provide a large size specimen to meet study requirements.

Approximately two specimens will be obtained from the buccal surface of each human or bovine tooth. For the 4 × 4 mm specimens, longitudinal sections approximately 3 mm in thickness will be made parallel to the selected tooth surfaces. The tooth sections will then be cut into 4 mm × 4 mm specimens using a Buehler Isomet low-speed saw. Each block will be ground and polished to create flat surfaces [Zero et al., 1990]. - For the 4 mm round specimens, a core of enamel 4 mm in diameter will be prepared from each bovine tooth by cutting perpendicularly to the buccal surface with a hollow-core diamond drill bit.

The square and round specimens will be ground and polished to create planar parallel dentin and enamel surfaces. All grinding/polishing will be done on a polishing surface moistened with deionized water (dw). The dentin side will be ground flat using 500 grit silicon carbide paper, followed by grinding and polishing of the enamel side. A small orientation cut will be placed on each block (see Figure 2 and 3). The enamel surface of each specimen will be ground using 1200 grit silicon carbide paper followed by 2400 and then 4000 grit silicon carbide paper. After the grinding procedures are completed, the enamel specimens will be sonicated in deionized water (dw) for two minutes and then placed under running dw for three minutes. The polishing step will involve the use of a 1 micrometer (µm) diamond suspension on a polishing cloth. The enamel specimens will then be rinsed under a steady stream of dw, sonicated for two minutes in 2% microliquid soap and then rinsed again with dw for three minutes. Resulting specimens will have a thickness range of 1.8 to 2.2 mm. The specimen will have a minimum polished surface of 3 mm × 3 mm in the center of the enamel surface.

Figure 2

4 x 4 mm Human Enamel Specimen

[figure not shown]
[figure not shown]

Figure 3

4 mm Round Bovine Enamel Specimen

6.2 Lesion Creation

The square and round enamel specimens will be partially demineralized using a modification of the method described by White [1987]. The 4 x 4 mm human enamel specimens will be immersed for 24 and the 4 mm round bovine specimens will be immersed for 18 hours at 37° C under static conditions in 40 ml of an acid buffer (0.05 mol/L lactate), 50% saturated with respect to hydroxyapatite and with 0.2% (wt/vol) carbopol 907 (BF Goodrich Co., USA) added (pH adjusted to 5.0 using KOH), and then rinsed thoroughly with deionized water. The demineralized enamel specimens will then be stored in a moist environment to prevent dehydration.

6.3 Lesion Quality

Lesions will be inclined towards an overhead light until a reflection is obtained. Acceptable lesions with an intact surface-zone will have a continuous, uniform shiny surface, with no matt areas. Lesions with matt area(s) will be rejected. The following criteria will be used to select specimens for inclusion in the study:

- The lesioned areas of each specimen should be of equal and uniform opacity; and
- The lesioned areas of each specimen should possess a surface shine when exposed to light, thereby indicating an intact surface.

6.4 Efficacy Measurements and Evaluations

6.4.1 Surface Microhardness

The SMH test will be used to assess changes in the mineral status of partially demineralized enamel specimens. SMH will be measured using a Wilson 2100 Hardness Tester. Each enamel specimen will be secured on a 1-inch square acrylic block with sticky wax and then placed on the microhardness tester. Five baseline indentations spaced 100 µm apart will be placed with a Knoop diamond under a 50 gram load in the center of a flattened, polished sound enamel specimen. SMH will be determined by measuring the length of the indentations using Wilson 2100 - Clemex CMT Software (version 6.0.011). For enamel specimens to be acceptable for use in the study, the mean of the five baseline indentation length must be $43 \pm 3 \mu\text{m}$ with a standard deviation of $\leq 3\mu\text{m}$.

After in vitro demineralization, the enamel specimens will be again SMH tested by placing five indentations 100 µm to the left of the baseline indentations (see Figures 2 and 3). To qualify for the study, the mean ($n = 5$) indentation lengths of the partially demineralized specimens must be $120 \pm 20 \mu\text{m}$ with a standard deviation of $\leq 10\mu\text{m}$. After 14 days of intra-oral exposure the enamel specimens will be again SMH-tested by placing five indentations 100 µm to the right of the baseline indentations (see Figure 2 and 3). The extent of remineralization will be calculated based on the method of [Gelhard et al., 1979].

$$\%SMH \text{ recovery} = (D1-R)/(D1-B) \times 100$$

B = indentation length (µm) of sound enamel specimen at baseline

D1 = indentation length (µm) after in vitro demineralization

R = indentation length (µm) after intra-oral exposure.

6.4.2 Enamel Fluoride Uptake

The microdrill enamel biopsy technique as described by [Sakkab et al., 1984] will be used to analyze the fluoride content of the partially demineralized enamel specimens. Each enamel specimen will be mounted perpendicular to the long axis of a drill bit attached to a specially designed microdrill, and drilled to a depth of ~100 µm through the entire lesion (four cores per specimen; see Figures 2 and 3).

The drilling and sample collection will be performed in a static-controlled atmosphere to prevent loss of enamel powder due to charging effects. The enamel powder sample, pooled from the four drilling samples, will be transferred to an analyzer cup cap. 20 microliters (µl) of 0.5 Molar (M) Perchloric Acid (HClO₄) will be added to the enamel powder and the cap gently swirled to dissolve the powder. To the analyzer cap containing the 20 µl of HClO₄/enamel powder, 40 µl of citrate/ ethylene-diamine-tetraacetic acid (EDTA) buffer and 40 µl of de-ionized water will be added and immediately analyzed for fluoride content using a fluoride specific electrode and pH/Ion meter. The diameter of the drill hole will be determined using a calibrated microscope interfaced with an image analysis system. The amount of fluoride-uptake by enamel will be calculated based on the amount of fluoride divided by the area of the enamel cores and expressed as µg F/cm².

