Over the past 10 years we have been experiencing increasing difficulty in recruiting subjects with mandibular partial dentures that meet our inclusion criteria. One of the reasons for the failure is the lack of sufficient room in the posterior buccal flange area of the subjects' partial dentures to accommodate two 4 × 4 mm enamel specimens. In an effort to improve subject recruitment we have redesigned the model so that the enamel specimens (4 mm round) are placed in the posterior denture tooth area of their denture and thus eliminate the requirement for having sufficiently large buccal flange area. We have already identified several potential subjects that only qualify for specimen placement in denture teeth and not in the buccal flange area. We have already successfully conducted an in vitro feasibility exercise to demonstrate the practicality of this technique. Furthermore, we have been placing specimens in the denture teeth location for several other in situ model studies including studies using our new biofilm model and this has not presented to be a problem for the subjects. The alteration of the denture teeth does not affect the occlusal part of the artificial tooth and thus does not alter a functional part of the denture.

An additional aspect of the modified model will be to use bovine enamel and not human enamel as has been our usual practice. We are facing increasing difficulty in obtaining a supply of human teeth for our research studies due to a decreasing supply and anticipated regulatory changes requiring informed consent. Most in situ model systems use either bovine or human teeth as the hard tissue substrate. From the perspective of clinical relevance, human teeth would be the most appropriate to use (Zero, 1995). Bovine enamel are known to have structural and chemical differences and to be more porous than human enamel (Lippert et al., 2013) and it is more vulnerable to acid dissolution than human enamel in an artificial caries model systems (Featherstone & Mellberg, 1981; Lippert et al., 2013; Lippert & Lynch, 2014). However, the resulting lesions are practically indistinguishable from each other (Lippert & Lynch, 2014), and these differences result in quantitative differences and not qualitative differences in their response in in situ model studies (Mellberg, 1992; Lippert & Hara, 2012). Bovine enamel can therefore be considered an acceptable alternative to human enamel.

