4. TEST TREATMENTS

The following products applied with a provided, marketed toothbrush will be used in this study:

1. 0 ppm F (placebo, negative control)
2. 250 ppm F as NaF (dose-response control)
3. 500 ppm F as NaF (dose-response control)
4. 1100 ppm F as NaF (positive control)

The test products will be provided by GlaxoSmithKline as part of the ISS funding mechanism using their Sensodyne sodium fluoride/silica toothpaste base formulation. The test products and fluoride-free washout toothpaste will be supplied in plain white tubes. Each tube will have a study label affixed. Each study label will contain, but not be limited to, protocol number, product code letter (for treatment products only), directions for storage, emergency contact telephone number and "For Clinical Trial Use Only".

Care should be taken with the supplied study products and their labels so that they are maintained in good condition. It is important that all labels remain intact and legible for the duration of the trial. Subjects should be instructed to not remove or deface any part of the study label.

Subjects will also receive a fluoride-free washout toothpaste and standard toothbrush for home use during the 2 to 3 day lead in period.

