7. STATISTICAL ANALYSES AND SAMPLE SIZE JUSTIFICATION

7.1 Statistical Analyses

The mean % SMH recovery will be calculated using the five sets of indentations within each enamel specimen. The mean fluoride uptake will be calculated using the four samples within each enamel specimen. The mean % SMH recovery, mean fluoride uptake, mean acid resistance and mean ΔZ , L, SZ_{max} will be computed for the two enamel specimens within a subject for each specimen location (buccal flange or tooth) by treatment; if a subject is missing an enamel specimen, the available enamel specimen will be used. Analyses of fluoride uptake will be performed after using a natural logarithm transformation because the measurements generally are not normally distributed. The validation of the new model will involve two types of evaluations. 1) Analysis level evaluation: The treatments will be compared using analysis of variance models (ANOVA) suitable for a crossover study. The models will include random effects for subject and fixed effects for study period, product, specimen location, and the location-by-product interaction. The random effects will model the correlation and variances over time within a location and the correlation between locations. The primary comparisons of interest will be to determine if the specimens placed in the tooth find the same comparisons to be statistically significant as the specimens placed in the buccal flange. In addition, although likely to be underpowered, the analyses will also include an evaluation of the equivalence of the two locations. This will involve calculating a 95% confidence interval for the ratio between the tooth and buccal flange locations for the relative difference between treatments (treatment difference divided by the positive control mean). A 5% significance level will be used for all tests. No alpha-level adjustments for multiple comparisons adjustments will be applied. 2) Data level evaluation: Agreement between the data from the tooth and buccal flange locations will be evaluated using Bland-Altman plots and intraclass correlation coefficients (ICCs).

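### Fluoride uptake is measured as total fluoride content with no stated background correction, so if native fluoride differs between human and bovine enamel, the between-location comparison would be distorted even with identical uptake

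*Combined protocol and SAP*

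**What the plan says.** Under section 6.4.2 of the protocol, the microdrill biopsy "will be used to analyze the fluoride content of the partially demineralized enamel specimens" after intra-oral exposure. Enamel powder is drilled to about 100 µm through the whole lesion, dissolved and assayed. The reported quantity is then defined: "The amount of fluoride-uptake by enamel will be calculated based on the amount of fluoride divided by the area of the enamel cores". Neither this section nor section 7.1 describes a pre-exposure biopsy, an unexposed reference lesion or a subtraction. By contrast, the hardness outcomes in sections 6.4.1, 6.4.3 and 6.4.4 are all computed from each specimen's own pre-exposure readings.

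On scale, section 7.1 states: "Analyses of fluoride uptake will be performed after using a natural logarithm transformation because the measurements generally are not normally distributed". The model has "fixed effects for study period, product, specimen location, and the location-by-product interaction". The main evaluation is to "determine if the specimens placed in the tooth find the same comparisons to be statistically significant as the specimens placed in the buccal flange". A secondary equivalence evaluation takes the tooth/flange ratio of the "relative difference between treatments (treatment difference divided by the positive control mean").

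Section 2 puts human enamel in the buccal flange and bovine enamel in the denture teeth, so location and species cannot be separated. Section 1 acknowledges: "Bovine enamel are known to have structural and chemical differences and to be more porous than human enamel". It does not mention native fluoride for either substrate.

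**The concern.** The study asks whether the modified model reproduces the fluoride dose response of the existing one. Within one substrate, a constant native fluoride content is only an offset. Between substrates, the offset can differ, and neither the log contrast nor a difference divided by the positive control mean removes it.

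Nothing in the plan makes native fluoride equal or checks it. Tooth selection (section 6.1), lesion quality (6.3) and the hardness limits (6.4.1) do not screen for fluoride. The lesions are also formed over different times, 24 hours for human and 18 hours for bovine specimens (6.2). For EFU, the plan could therefore report a between-model difference in dose response that reflects background only, or could mask a real one.

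**Working it through.** **The plan's own figure.** The only quantitative target is in section 7.2: 24 completers, SD of treatment differences 10, difference 6 in % SMH recovery, two-sided 5%, 80% power. A paired noncentral t with 23 degrees of freedom and standardized difference 6/10 = 0.6 gives 80.4%, so the figure is reproduced. It concerns hardness and is unaffected by this point. The documents give no SD, effect or native level for EFU.

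**Formulas.** Let N be native fluoride and U uptake, both in µg F/cm². The assay returns N + U.

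- Log contrast, 1100 against 0 ppm F: ln[(N + U1100)/(N + U0)]. This depends on N.
- Relative difference on untransformed means: (U1100 − U0)/(N + U1100). N cancels in the numerator but stays in the denominator.
- Tooth/flange ratio of relative differences when uptake is identical: (N_human + U1100)/(N_bovine + U1100).

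**Inputs, all assumed.** Uptake is identical in both locations: 2 at 0 ppm and 12 at 1100 ppm F.

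| N human, N bovine | Fold, human | Fold, bovine | False ln interaction | Tooth/flange ratio |
|---|---|---|---|---|
| 3, 3 | 15/5 = 3.00 | 15/5 = 3.00 | 0 | 1.00 |
| 3, 1 | 15/5 = 3.00 | 13/3 = 4.33 | 0.37 | 15/13 = 1.15 |
| 6, 2 | 18/8 = 2.25 | 14/4 = 3.50 | 0.44 | 18/14 = 1.29 |
| 9, 1.5 | 21/11 = 1.91 | 13.5/3.5 = 3.86 | 0.70 | 21/13.5 = 1.56 |
| 1, 3 (reversed) | 13/3 = 4.33 | 15/5 = 3.00 | −0.37 | 13/15 = 0.87 |

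The interaction is ln(bovine fold/human fold). The raw 1100-minus-0 difference is 10 in every row.

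A second assumed set, uptake 0 and 4 in arbitrary units, behaves the same way. Native (2, 1) gives ln 5 − ln 3 = 0.51 and a ratio of 6/5 = 1.20. Native (4, 1) gives ln 5 − ln 2 = 0.92 and a ratio of 8/5 = 1.60.

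**Does the offset change which comparisons are significant?** Paired log-scale tests were simulated with n = 24, lognormal uptake with CV 1.0, half the log variance shared within subject, and constant N (all assumed). For uptake 2 against 4, raising N from 1 to 9 shrinks the mean log difference from 0.45 to 0.15, and its SD from 0.55 to 0.21. Power moves only from 97% to 93%. For 5.5 against 8 it moves from about 55% to 50%. For 2 against 12 it is about 100% at both values of N. Effect and noise shrink together, so significance hardly changes.

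**Check of the remedy.** Add assumed uptakes of 4.5 and 7 at 250 and 500 ppm F. The fractions of the 1100-minus-0 span are (4.5 − 2)/10 = 0.25 and (7 − 2)/10 = 0.50 for any N, so the tooth/flange ratio is 1.00. If bovine uptake is 1.5 times human throughout (3, 6.75, 10.5, 18), the span is 15 instead of 10. The fractions are still 3.75/15 = 0.25 and 7.5/15 = 0.50. A comparison of raw differences alone would show 15/10 = 1.5.

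**The case against.** Several points on the other side have force.

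- A reader might infer that human and bovine specimens *will* show different log-scale responses. The documents do not support that. Section 1 mentions chemical differences but not fluoride, and with equal native content the distortion is exactly zero. This stands; the point is conditional.
- A reader might also infer that one substrate would yield more significant comparisons purely because of background. The simulation does not bear this out for a constant offset, so the main evaluation in section 7.1 is little affected by it. If native fluoride varies between specimens (assumed log SD 0.3, uptake 2 against 4), log-scale power does fall, from 95% at N = 1 to about 40% at N = 9. Raw-scale power falls similarly, from 86% to about 40%. That loss comes from added noise, which subtracting placebo does not cure.
- The cited biopsy method, or the procedures that section 5.1 says are on file, may include a background correction. Neither can be checked here. The supportable statement is that the protocol describes none.
- The two models are compared as packages, and section 1 already expects quantitative rather than qualitative differences between substrates. The interaction is not a pass/fail criterion, and section 7.1 calls the equivalence evaluation likely to be underpowered. This limits the consequence. It does not help a reader tell background from uptake when the EFU ratio departs from 1.
- Moving everything to raw differences would cost power (about 87% against 93% to 97% in the constant-offset example) and would flag a merely proportional difference in uptake. This stands, and is why the log analysis should be kept.

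**Conclusion.** The concern holds in conditional form. As written, EFU is total fluoride per area, and the planned between-location measures do not remove an additive background. If native fluoride differs between substrates, identical uptake gives a false log-scale interaction of 0.37 to 0.70 and a tooth/flange ratio of 1.15 to 1.56 on the main assumed inputs. The signs reverse if bovine enamel carries more native fluoride. These figures illustrate the mechanism and do not predict its size, because no native or uptake value is in the documents. The ratio is worked on untransformed means; section 7.1 does not say which scale it uses for EFU. The within-location significance comparisons and the sample size are not called into question. This is a cheap improvement to the interpretation of one outcome.

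**What to change.** Keep the log-scale analysis, including the within-location significance comparisons. In section 7.1, add a placebo-referenced EFU comparison between locations:

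- For 250 and 500 ppm F, express (dose minus 0 ppm) as a fraction of the same location's (1100 minus 0 ppm) difference, on the raw scale.
- Report the tooth/flange ratio of these fractions with a bootstrap interval that resamples whole subjects, so that periods and both locations stay together.
- Report the raw 1100-minus-0 difference for each location beside it. The span measure equals 1 at 1100 ppm F by construction and cannot compare that contrast.
- State in section 6.4.2 how native fluoride is handled. If it is not removed, call the measured quantity fluoride content.

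The 0 ppm arm is already measured in both substrates in the same subjects, so no new specimens are needed. The cost is a little extra analysis and possibly wider EFU intervals. New specimens are placed in each period, so variation in native fluoride between specimens is removed only on average.
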